#### 18.5. PHYSICAL EXAMINATION

As all physical and neurological findings will be recorded as AEs, no specific analysis of physical and neurological examination will be performed.

#### 18.6. OTHER SAFETY ASSESSMENTS

##### 18.6.1. COLUMBIA SUICIDE SEVERITY RATING SCALE (C-SSRS)

The C-SSRS is a tool designed to systematically assess and track suicidal behavior and suicidal ideation throughout the study. The strength of this suicide classification system is in its ability to comprehensively identify suicidal events while limiting the over-identification of suicidal behavior. The C-SSRS Baseline/Screening Version is used at the screening visit of studies SEP380-301. The C-SSRS Since Last Visit Version is used from Visit 2 and onward in studies SEP380-301, and at all visits in extension study SEP380-303. Subjects with Type 4 (active suicidal ideation with some intent to act, without specific plan) or Type 5 (active suicidal ideation with specific plan and intent) suicidal ideation during the study will be discontinued from the study and referred to a mental health professional.

C-SSRS includes two main sections: Suicidal Ideation and Suicidal Behavior.

The following outcomes are C-SSRS categories and have binary responses (yes/no). The categories are re-ordered from the scale to facilitate the definitions of the C-SSRS endpoints, and to provide clarity

in the presentation of the results.

- Suicidal ideation is measured by 5 categories, representing 5 subtypes of suicidal ideation with increasing severity:
  - Category 1: Wish to be Dead
  - Category 2: Non-specific Active Suicidal Thoughts
  - Category 3: Active Suicidal Ideation with Any Methods (Not Plan) without Intent to Act
  - Category 4: Active Suicidal Ideation with Some Intent to Act, without Specific Plan
  - Category 5: Active Suicidal Ideation with Specific Plan and Intent
- Suicidal behavior is measured by 5 categories, representing 5 subtypes of suicidal behavior:
  - Category 6: Preparatory Acts or Behavior
  - Category 7: Aborted Attempt
  - Category 8: Interrupted Attempt
  - Category 9: Actual Attempt (non-fatal)
  - Category 10: Completed Suicide

The 10 categories above are mutually exclusive. Subjects will be counted in the most severity category for which they have an event.

Self-injurious behavior without suicidal intent is a non-suicide-related C-SSRS outcome, and also has a binary response (yes/no).

For the purpose of C-SSRS analysis, “DB Baseline”, “OL Baseline”, and the overall “post-OL Baseline Extension” periods are defined as follows.

Time point	Study Visit	C-SSRS Version	Derivation Rule
DB Baseline	Visit 1 of study SEP380-301	Baseline/Screening – Past 1 Month for Suicidal Ideation / Past 6 Months for Suicidal Behavior	Most severe outcome
	Visit 2* of study SEP380-301	Since Last Visit	
OL Baseline	Week 6/Visit 6** of study SEP380-301	Since Last Visit	As collected for that visit
Post-OL Baseline Extension Period	All post-OL Baseline extension study visits up to and including 7 days post the last OLE dose, including unscheduled visits	Since Last Visit	Most severe outcome

\* Note: The Visit 2 C-SSRS assessment must be administered prior to the first dose of SEP380-301 study medication in order to be used in the C-SSRS DB Baseline derivation.

\*\*Note: The Visit 6 C-SSRS assessment must be administered prior to the first dose of SEP380-303 extension study medication in order to be used as the C-SSRS OL Baseline. In the rare event where the Visit 6 assessment is administered after the first dose of SEP380-303 extension study medication, take the assessment from the previous visit as the OL Baseline.

The following C-SSRS composite endpoints will be derived for each time point of interest (i.e., DB Baseline, OL Baseline, overall post-OL Baseline extension period, and each OLE study visit) as follows:

- Any suicidal ideation: A “yes” answer to any one of the 5 suicidal ideation questions on C-SSRS (Categories 1-5).
- Any suicidal behavior: A “yes” answer to any one of the 5 suicidal behavior questions on the C-SSRS (Categories 6-10).
- Any suicidality: A “yes” answer to any one of the 10 suicidal ideation and behavior questions on the C-SSRS (Categories 1-10).

For each subject, the suicidal ideation score at each time point of interest (i.e., DB Baseline, OL Baseline, overall post-OL Baseline extension period, each OLE study visit, and LOCF) is defined as the maximum suicidal ideation category (1-5) present for the time point of interest. If no ideation is present a score of 0 is assigned.

The number and percentage of subjects with any suicidality, any suicidal ideation and subtypes of ideation, any suicidal behavior and subtype of behavior, and any non-suicidal self-injurious behavior will be presented for:

- DB Baseline (as defined above)
- OL Baseline (as defined above)
- Overall post-OL Baseline extension period (as defined above)
- Each scheduled OLE study visit (starting from Visit 2E)

Shift in suicidal ideation score from DB Baseline to the overall post-OL Baseline extension period, each scheduled OLE study visit (starting from Visit 1E), and LOCF, and shift from OL Baseline to each scheduled post-OL Baseline extension study visit (starting from Visit 2E), and LOCF, will be presented.

Intensity of ideation for the most severe ideation subtype is measured in terms of frequency, duration, controllability, deterrents, and reasons for ideation. Each is measured with responses ranging from 1 to 5 for frequency and duration, and from 0 to 5 for controllability, deterrents, and reasons for ideation.

The ideation intensity total score is the sum of responses to the five items and can range from 2 to 25 for subjects with endorsed suicidal ideation. For subjects with endorsed suicidal ideation, if one or more of these five items are missing at an assessment, the total score will be set to missing. If a subject did not endorse any suicidal ideation, a score of 0 for the ideation intensity total score will be given.

Actual lethality associated with actual attempts is rated on a 6-point scale from 0 = ‘No physical damage or very minor physical damage’ to 5 = ‘Death’. Potential lethality of actual attempts (if actual lethality = 0) is rated on a 3-point scale from 0 = ‘Behavior not likely to result in injury’ to 2 = ‘Behavior likely to result in death despite available medical care’.

Responses to each C-SSRS question will be listed. The ideation intensity total score and the actual lethality and potential lethality of actual attempts will only be presented in data listings.

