AEs in each category). The number and proportion of subjects with one or more AEs within a system organ class (SOC) and by preferred term will be presented by analysis group as well. The incidence of AEs of special interest, including but not limited to hyperprolactinemia related AEs, will be summarized for overall and by gender, as appropriate. Incidence of post-treatment adverse events (defined as an AE with a start date after the date of last dose of study drug through the last contact/visit in the follow-up period) will be summarized separately for subjects in the follow-up population.

For safety assessments, descriptive statistics will be provided for observed values and changes from DB Baseline and OL Baseline, respectively, by study visit and analysis group for the continuous variables. Frequencies and percentages will be reported for categorical variables by study visit and analysis group. The markedly abnormal values for selected safety parameters will be summarized, as appropriate.

The number and percentage of subjects with suicidal ideation and/or suicidal behavior, emergence or worsening of suicidal ideation or suicidal behavior will be summarized by analysis group for the open-label treatment period.

The PWC score will be summarized by presenting descriptive statistics of observed values and changes from Week 52/EOT by analysis group based on the follow-up population.

Descriptive statistics of observed values and changes from DB Baseline and OL Baseline will be summarized by study visit and analysis group for effectiveness parameters (continuous). At a visit in the extension study, responders relative to DB Baseline are defined as those who show a 50% or more reduction (ie, improvement) from DB Baseline in MADRS total score. At a post-OL Baseline visit, responders relative to OL Baseline are defined as those who show a 50% or more reduction (ie, improvement) from OL Baseline. Remitters at any visit are defined as subjects with a MADRS total score of ≤ 12 . Frequencies and percentages of MADRS responders relative to both DB Baseline and OL Baseline, and frequencies and percentages of remitters will be summarized over time by analysis group.

Sample Size Consideration: Assuming a completion rate of 85% in the lead-in study of SEP-4199 CR and an 80% rollover rate of completers from that study to the current extension study, it is estimated that approximately 355 subjects will be enrolled.

				12-Month	n Open-Lab	el Treatmen	nt Period		

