15.4.3.7. Columbia-Suicide Severity Rating Scale (C-SSRS)

The number and percentage of subjects with suicidal ideation, suicidal behavior, emergence or worsening of suicidal ideation or suicidal behavior will be summarized by analysis group for the open-label extension treatment period.

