## 4.7. CHANGES TO ANALYSIS FROM PROTOCOL

Because of the small sample size due to study early termination, the following main changes will be made for this study:

- Only 2 treatment groups will be formed based on a subject's previous participation in the lead-in study of SEP-4199 CR (SEP-SEP: previously randomized to any SEP-4199 CR dose group and PBO-SEP: previously randomized to placebo).
- No subgroup summaries will be performed.
- No summaries using Follow-up population will be performed.
- Except for PWC, follow-up period summaries will not be performed, PWC will be summarized by Safety population.
- AE will not be summarized by high-level term (HLT).
- No Kaplan-Meier curves will be plotted for time to discontinuation and time to the earliest onsets of the selected AESI. The Kaplan-Meier estimation will also not be performed.
- To be consistent with AIMS and BARS, MSAS will be summarized by total score.

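### SAP 18.6.1 omits the protocol's count of subjects with emergent or worsened suicidality and has no overall-period comparison with OL Baseline

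*SAP*

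**What the plan says.** The protocol's statistical section on the C-SSRS (15.4.3.7) lists, beside ideation and behavior themselves, that "emergence or worsening of suicidal ideation or suicidal behavior will be summarized by analysis group". The synopsis makes the same commitment: "emergence or worsening of suicidal ideation or suicidal behavior will be summarized by analysis group for the open-label treatment period".

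SAP 18.6.1 plans the following:

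- **Incidence.** Number and percentage with any suicidality, any ideation, any behavior and the subtypes, at DB Baseline, at OL Baseline, over the whole extension period (most severe outcome, unscheduled visits included) and at each visit.
- **Shift from DB Baseline.** "Shift in suicidal ideation score from DB Baseline to the overall post-OL Baseline extension period", and also to each visit from 1E and to LOCF.
- **Shift from OL Baseline.** "shift from OL Baseline to each scheduled post-OL Baseline extension study visit (starting from Visit 2E), and LOCF, will be presented". The overall period is not named here.
- **Behavior.** No shift and no change category of any kind.
- **Listings.** Every C-SSRS response.

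DB Baseline is the most severe outcome of two lead-in assessments: Visit 1, with a recall window of "Past 1 Month for Suicidal Ideation / Past 6 Months for Suicidal Behavior", and Visit 2. OL Baseline is the single Visit 6 assessment of the lead-in study, as collected.

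SAP 4.7 introduces its list with "Because of the small sample size due to study early termination, the following main changes will be made for this study". None of its seven bullets concerns the C-SSRS.

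**The concern.** Suicidality on long-term treatment is a stated safety objective in both documents. The protocol's count answers a direct question: how many distinct subjects became suicidal, or more so, while on the extension? SAP 18.6.1 neither defines nor tabulates that count, and does not say it was dropped.

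The reference matters because the two baselines mean different things. DB Baseline is a worst-case look-back taken at entry to a trial in acute bipolar depression, so it sets a high bar for calling anything worse. OL Baseline describes the subject on entry to the extension. For PBO-SEP subjects it is also the last assessment before their first SEP-4199 dose, so a worst-case comparison with it is the closest this uncontrolled study comes to a before-and-after-drug view.

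**Working it through.** No power or sample-size figure enters this point, so there is no stated figure to reproduce. The check sets the planned tables side by side, then counts score patterns.

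**Step 1. What each planned output can give**

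| Output | Counts distinct subjects over the whole period? | Separates new or worse from pre-existing? |
|---|---|---|
| Overall-period incidence rows | Yes | No |
| Overall ideation shift from DB Baseline | Yes | Only against DB Baseline |
| By-visit ideation shift from OL Baseline | No | Yes, one visit at a time |
| LOCF ideation shift from OL Baseline | Last value only | Only if still present at the end |
| Any shift for behavior | Not planned | Not planned |

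*Incidence rows.* Let *a* subjects have ideation at OL Baseline and *b* in the extension, out of *N*. The number with both lies between max(0, a + b − N) and min(a, b). The number with emergence is *b* minus that, so the tables fix it only to the range max(0, b − a) to min(b, N − a). The same holds for behavior.

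*By-visit shifts.* If *v_j* subjects show a worsening at visit *j*, the number of distinct subjects who worsened at a scheduled visit lies between the largest *v_j* and the sum of the *v_j*. SAP 7.4 also keeps unscheduled assessments out of by-visit tables as a time point, so a worsening seen only at an unscheduled visit is missing from these tables unless it supplies the LOCF value.

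**Step 2. One subject followed through the tables**

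Take DB Baseline 3, OL Baseline 0 and a worst extension score of 2.

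- Overall incidence: counted under any suicidality, any ideation and category 2.
- Overall shift from DB Baseline: 3 to 2, an improvement.
- By-visit shift from OL Baseline: 0 to 2 if the score came from a scheduled visit, absent if it came from an unscheduled one.
- LOCF shift from OL Baseline: 0 to 0 if the last score is 0.

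A second subject with scores 3, 2 and 2 falls in the same overall-period incidence rows and the same DB shift cell. The first subject has ideation that is new since OL Baseline, and the second is unchanged. The overall-period tables do not tell them apart.

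**Step 3. Count of possible patterns**

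Inputs: DB Baseline score 0–5; OL Baseline score 0–3, because protocol exclusion criterion 7 bars ideation items 4 and 5 at Visit 6; worst extension score 0–5.

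- All patterns: 6 × 4 × 6 = 144.
- Worse than OL Baseline: for OL = 0, 1, 2, 3 there are 5, 4, 3, 2 higher scores. That is 14, and 14 × 6 DB scores = 84.
- Of these, not worse than DB Baseline: 15 + 10 + 6 + 3 = 34, and 34/84 = 40%.
- With OL Baseline 0 (emergence): 15 of 30 = 50%.

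The overall shift from DB Baseline therefore shows 84 − 34 = 50 of the 84 worsening patterns as worse. A shift from OL Baseline would show all 84.

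**Step 4. Practice elsewhere in the same SAP**

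SAP 18.6.3 (AIMS) and 18.6.5 (MSAS) plan category shifts to the overall extension period from both DB and OL Baseline. SAP 18.6.2 counts treatment-emergent mania at any time in the study. The C-SSRS section has no equivalent against OL Baseline and gives no reason.

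**The case against.** The strongest reply is that the protocol defines neither emergence nor worsening and names no baseline for them. Protocol 15.4 makes DB Baseline the usual reference for changes and adds OL Baseline where relevant. On that reading, the ideation count can be taken from the planned overall shift from DB Baseline: subjects moving from 0 to a positive score, or to a higher one. This stands for ideation against DB Baseline. It does not supply the comparison with OL Baseline, and it supplies nothing for behavior, which the protocol names.

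Second, with 64 subjects enrolled, no inference planned and every response listed, the count can be made by hand. That is true, but a promised safety summary should not depend on each reader rebuilding it from listings.

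Third, SAP 4.7 claims only to list main changes, and the table templates are separate documents not available here. The list therefore need not be exhaustive and the templates could contain more. Even so, the SAP text gives no definition that a template could follow, while 4.7 does record smaller changes, such as dropping AE summaries by high-level term.

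Fourth, ideation items 4 and 5 lead to discontinuation and an associated AE under protocol 11.4.6.1 and 13.1, so those events should reach other tables. That rule does not name items 1–3 or suicidal behavior.

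**Conclusion.** The point holds as an undocumented departure from the protocol. No emergence or worsening count is defined, suicidal behavior has no comparison with either baseline, and ideation has no overall-period comparison with OL Baseline. The overall shift from DB Baseline can show new ideation in the extension as unchanged or improved.

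A reader might infer more, and the documents do not support it:

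- *That suicidal events are hidden.* They are not. Every event in the evaluation period enters the overall incidence rows, a scheduled-visit event also appears in that visit's tables, and all responses are listed. What is missing is the label of new or worse relative to OL Baseline.
- *That the rule "The 10 categories above are mutually exclusive" loses events.* Counting each subject in the most severe category can empty lesser subtype rows. The composites are set by any positive answer and the ideation score by the maximum ideation category, so neither is reduced. This is a minor display matter and not part of the point.
- *That 40% of worsened subjects would be missed.* The 34 of 84 gives equal weight to every possible pattern. The documents give no score distribution, so the number of subjects affected is unknown and could be zero.

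The pattern count assumes that exclusion criterion 7 was applied at Visit 6. The worked example does not depend on that.

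**What to change.** In SAP 18.6.1, add for the overall extension period:

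1. The shift in worst ideation score from OL Baseline, beside the existing one from DB Baseline.
2. Number and percentage of subjects with emergence (none at baseline, any after OL Baseline) and with worsening (a more severe category than at baseline), for ideation and separately for behavior, against OL Baseline and against DB Baseline. State the denominator and whether emergent subjects are also counted as worsened.

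Reporting both references is useful because OL Baseline is a single assessment and DB Baseline a longer look-back. If the sponsor prefers not to add these counts, SAP 4.7 should record the omission and give the reason.

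The cost is one or two tables by the existing PBO-SEP, SEP-SEP and ALL EXT columns. The baseline and worst-period ideation scores and the behavior categories are already derived under SAP 18.6.1, and no new data are needed.

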### **18.6.2. YOUNG MANIA RATING SCALE (YMRS)**

The YMRS will be administered as a safety assessment and to inform the identification of treatment-emergent mania or hypomania.

The YMRS is a clinician-rated 11-item instrument used to assess the severity of mania in subjects with a diagnosis of bipolar disorder. The 11 items assess: Elevated Mood, Increased Motor Activity/Energy, Sexual Interest, Sleep, Irritability, Speech (Rate and Amount), Language/Thought Disorder, Content, Disruptive-Aggressive Behavior, Appearance, and Insight. The YMRS total score is the sum of the 11 individual items and ranges from 0 to 60. A higher score is associated with a greater severity of mania.

If one or more items are missing at a visit, the total score will be set to missing.

YMRS is assessed at Week 2 and monthly and at these study visits: from Visit 1E (coinciding with Visit 6 of SEP380-301) to Visit 15E.

Treatment-emergent mania or hypomania is defined as a YMRS total score  $\geq 16$  at any 2 consecutive post-OL Baseline visits or at the final visit, or an AE of mania or hypomania during the post-OL Baseline extension period (including both the OLE treatment period and the OLE follow-up period up to and including 7 days post the last OLE dose).

The DB Baseline and OL Baseline YMRS total score will be derived as described in [Section 7.2](#). The change from DB Baseline and OL Baseline in YMRS total score will be derived as described in [Section 7.7](#).

The observed values of YMRS total score at both the DB Baseline and the OL Baseline, and at each scheduled OLE study visit (starting from Visit 2E) and LOCF, will be summarized descriptively.

Changes from DB Baseline in YMRS total score will be summarized for each scheduled OLE study visit (starting from Visit 1E) and LOCF. Changes from OL Baseline will be summarized for each scheduled post-OL Baseline extension study visit (starting from Visit 2E) and LOCF.

Frequency and percentage of subjects experiencing treatment-emergent mania at any time during the study will be presented by treatment group.

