11.4.6.2. Young Mania Rating Scale (YMRS)

The YMRS will be administered as a safety assessment and to inform the identification of treatment-emergent mania or hypomania.

The YMRS is a clinician-rated 11-item instrument used to assess the severity of mania in subjects with a diagnosis of bipolar disorder. The 11 items assess: Elevated Mood, Increased Motor Activity/Energy, Sexual Interest, Sleep, Irritability, Speech (Rate and Amount), Language/Thought Disorder, Content, Disruptive-Aggressive Behavior, Appearance, and Insight. The YMRS will be administered by a qualified rater at the site. Further information regarding administration of the YMRS, including rater training and qualification as well as recording of YMRS scores, will be provided in the Study Reference Manual.

Treatment-emergent mania or hypomania is defined as a YMRS total score \geq 16 at any 2 consecutive post-Baseline visits or at the final visit, or an AE of mania or hypomania.

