15.4.3.2. Treatment-Emergent Mania

Treatment-emergent mania is defined as a YMRS score of ≥ 16 on any 2 consecutive OL visits (ie, including OL Baseline visit for subjects previously randomized to SEP380-4199 CR group or excluding the visit(s) with study day \leq Day 1 for subjects previously randomized to placebo group) or at the final assessment in the OL treatment period, or any treatment-emergent AE of mania or hypomania. If a subject has reported no AE of mania or hypomania and has no YMRS assessment (including OL Baseline for subjects previously randomized to SEP380-4199 CR group or has no post-OL Baseline YMRS assessment for subjects previously randomized to placebo), incidence of treatment-emergent mania will be set to missing.

For YMRS total score, descriptive statistics will be provided for observed values and changes from DB Baseline and OL Baseline, respectively, by study visit and analysis group.

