### **3.2.2. OTHER SAFETY ENDPOINTS**

- The incidence of AESI including but not limited to hyperprolactinemia-related AEs
- Clinical laboratory evaluations (serum chemistry, hematology, thyroid panel, urinalysis)
- Clinical evaluation (vital signs including orthostatic effects, and 12-lead ECG measurements)
- Changes in prolactin values
- Changes in metabolic parameters (insulin, glucose, hemoglobin A1c (HbA1c), lipid panel)
- Change and percent change in body weight
- Change in body mass index (BMI)
- Incidence of treatment-emergent mania, defined as a YMRS total score  $\geq 16$  at post-Baseline visit (scheduled or unscheduled), or an adverse event of hypomania or mania
- Changes from Baseline in movement disorders scales: AIMS, BARS, and modified SAS
- Frequency and severity of suicidal ideation and suicidal behavior using the C-SSRS
- Change from Week 52/EOT (end of treatment) visit to the safety follow-up visit on the PWC

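### SAP 3.2.2 lists treatment-emergent mania as a single post-Baseline YMRS of 16 or more, but the only summary the SAP text describes (18.6.2) needs two consecutive visits or the final visit, so some listed events go uncounted

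*SAP*

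**What the plan says.** The documents give two definitions of one endpoint.

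- **Single-visit rule.** SAP 3.2.2 counts a YMRS total of 16 or more "at post-Baseline visit (scheduled or unscheduled), or an adverse event of hypomania or mania". Protocol 6.1 and the Synopsis carry the same wording.
- **Persistence rule.** SAP 18.6.2 counts a YMRS total of 16 or more "at any 2 consecutive post-OL Baseline visits or at the final visit, or an AE of mania or hypomania". Protocol 11.4.6.2 has nearly the same text: "at any 2 consecutive post-Baseline visits or at the final visit, or an AE of mania or hypomania". Protocol 15.4.3.2 also asks for two consecutive visits, "or at the final assessment in the OL treatment period, or any treatment-emergent AE of mania or hypomania".

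The planned output follows the persistence rule within SAP 18.6.2: "Frequency and percentage of subjects experiencing treatment-emergent mania at any time during the study will be presented by treatment group". No other part of the SAP text describes a mania summary; the table templates are separate and were not available.

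Protocol 15.4.3.2 adds two details that SAP 18.6.2 does not restate. Its qualifying open-label visits are defined as "including OL Baseline visit for subjects previously randomized to SEP380-4199 CR group", with a different start for prior-placebo subjects. And where there is neither a usable YMRS nor a mania AE, "incidence of treatment-emergent mania will be set to missing".

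SAP 18.6.2 sets an evaluation period that includes "the OLE follow-up period up to and including 7 days post the last OLE dose". The sentence does not make clear whether this governs the YMRS part or only the AE part. SAP 4.7, which lists the main changes from the protocol, mentions none of these points.

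**The concern.** A reader who takes the endpoint from SAP 3.2.2 will read the tabulated percentage as the share of subjects who ever reached 16 or had a mania or hypomania AE. The table described in 18.6.2 is narrower. It omits subjects whose score reached 16 once, before the final visit, without a matching AE.

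Monthly visits are several weeks apart, so an elevation that has gone by the next scheduled visit fails the two-visit test. Emergent mania is a named safety endpoint in a bipolar I study. Two programmers working from the same SAP could report different numbers, and nothing in 4.7 would tell a reader which rule was applied.

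**Working it through.** The plan states no figure on this point to reproduce. The check is a comparison of definitions, followed by simple arithmetic on size.

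**1. Nesting.** Two consecutive visits at 16 or more, or a final visit at 16 or more, always include at least one post-Baseline visit at 16 or more. The AE limb is common to both rules. So every 18.6.2 event is a 3.2.2 event, but not the reverse, and on the same denominator the 18.6.2 incidence cannot exceed that of 3.2.2.

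**2. Example subjects.** There is no mania or hypomania AE unless stated.

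| YMRS of 16 or more at | SAP 3.2.2 | SAP 18.6.2 | Protocol 15.4.3.2 |
|---|---|---|---|
| 6E only | event | not counted | not counted |
| 6E only, with an AE of hypomania | event | event | event |
| 6E and 7E | event | event | event |
| one unscheduled, non-final visit only | event | not counted | not counted |
| 14E only, 15E attended and below 16 | event | event if the final visit is 14E, otherwise not | event |
| OL Baseline and 2E only, prior SEP-4199 subject | event (2E) | not counted | event |
| no post-OL Baseline YMRS, prior-placebo subject | not addressed | not addressed | missing |

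**3. Isolated scores by position.** YMRS is scheduled at 2E to 15E, which is 14 post-OL Baseline visits. Assume all are attended and there is no AE. One isolated score then counts at 14 of 14 positions under 3.2.2 and at 1 of 14 (15E) under 18.6.2. If 14E is the final visit, the figures are 13 of 13 and 1 of 13.

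**4. Interval between paired scheduled visits (days, from the visit windows).**

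- 2E (12–16) to 3E (28–32): 28 − 16 = 12, up to 32 − 12 = 20.
- 3E (28–32) to 4E (55–65): 55 − 32 = 23, up to 65 − 28 = 37.
- 4E (55–65) to 5E (85–95): 85 − 65 = 20, up to 95 − 55 = 40. The same holds for each later monthly pair to 13E.
- 13E (325–335) to 14E (360–365): 360 − 335 = 25, up to 365 − 325 = 40. This uses the +5 window in the Synopsis, Protocol Table 2 and Protocol 11.6.14. The window paragraph of Protocol 7.1 and footnote a of SAP Appendix 7 print ±5, which gives 355 − 335 = 20, up to 40.
- 14E to 15E: 5 to 9 days for a completer who takes the last dose on the morning of 14E. This pair matters only if 15E qualifies.

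**5. Which visit is final.** Visit 15E falls 5 to 9 days after the last dose; days 5, 6 and 7 are inside the 7-day limit and days 8 and 9 are outside. The period named in 18.6.2 and the general cut-off in SAP 7.5 therefore allow 15E. Three places point instead to the treatment period: SAP 4.7 drops follow-up summaries except for PWC, SAP 7.3 stops LOCF at 14E, and Protocol 15.4.3.2 names the treatment period. The documents do not settle it.

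**6. Weight of one subject.** SAP 4.4 gives 64 enrolled.

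- ALL EXT: 1/64 = 1.6 points. For illustration, two or three uncounted subjects would be 2/64 = 3.1 or 3/64 = 4.7 points. The weight rises slightly if some enrolled subjects were not dosed.
- Group sizes are not given. If PBO-SEP is assumed to be a quarter to a half of the 64 (16 to 32), one subject is 1/16 = 6.3 to 1/32 = 3.1 points there, and 1/48 = 2.1 to 1/32 = 3.1 points in SEP-SEP.

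**The case against.** The best defence is that 18.6.2 is not a departure: it carries the core rule of both the YMRS section and the statistics section of the protocol. The outlier is a short endpoint bullet copied from the Synopsis and Protocol 6.1, and a one-line edit to 3.2.2 would remove the mismatch. The stricter rule is stated openly, no inference is planned (SAP 7.6), and nothing is hidden: observed YMRS is summarised by visit, listings include unscheduled data, and AEs of mania or hypomania count under both rules.

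Most of this stands, and it limits the severity. It does not remove the point. The SAP repeats both sides of the protocol's split without resolving it, and the by-visit summaries describe scores and changes rather than the number of subjects who ever reached 16.

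Three stronger readings are tempting but unsupported.

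- **Subjects without YMRS data and without an AE are counted as non-events.** SAP 18.6.2 does not say so. It fails to restate the set-to-missing rule; SAP 4.7 does not revoke that rule, and naming the Safety Population does not settle how an indeterminate subject is classed.
- **Unscheduled visits are excluded.** SAP 7.4 mainly governs by-visit summaries, and its silence on an any-time flag excludes nothing. SAP 18.6.2 leaves open whether an unscheduled visit can form or break a pair; the C-SSRS section, by contrast, includes unscheduled visits expressly.
- **Dropping OL Baseline is an SAP departure from the protocol.** It differs from 15.4.3.2 but agrees with 11.4.6.2, so the split lies within the protocol.

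**Conclusion.** The contradiction is real. SAP 3.2.2 lists one endpoint and SAP 18.6.2 tabulates a narrower one, with no note in 4.7. The direction is certain on a common denominator: the tabulated incidence equals or falls below that of the listed endpoint. The size is not known. It is zero if every isolated non-final score comes with a mania or hypomania AE; otherwise it is 1.6 points of ALL EXT per subject, on 64 enrolled. The by-group weights rest on an assumed split.

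The further gaps concern the final visit, the evaluation period for the YMRS part, unscheduled visits, OL Baseline and the set-to-missing rule. They are matters left unstated or unreconciled, not shown errors in a count. A reader might infer that the SAP conceals mania cases; the AE tables and the listings show otherwise. What is absent is a count of subjects who qualify on a single YMRS score alone.

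Severity is minor to should-fix. The effect is on how a descriptive safety count is defined and labelled, not on any inference.

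**What to change.** In SAP 18.6.2, tabulate both definitions as labelled rows:

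- (a) YMRS of 16 or more at any post-OL Baseline visit, scheduled or unscheduled, or an AE of mania or hypomania;
- (b) YMRS of 16 or more at two consecutive visits or at the final visit, or such an AE.

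State which row is the endpoint and align SAP 3.2.2 with it. Then reconcile the following with Protocol 15.4.3.2: whether the final visit is 14E or 15E, which period applies to the YMRS part, whether an unscheduled visit can form or break a consecutive pair, how OL Baseline is treated for prior SEP-4199 subjects, and whether the set-to-missing rule applies. Record any remaining departure in SAP 4.7.

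The cost is one derived flag and one table row from data already collected, plus a few lines of text in 3.2.2, 18.6.2 and 4.7. The downside is that row (a) may include brief elevations that are not clinical episodes, and two rows need clear labels to avoid confusion.
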